8.7.3.4 Main Estimation of Phase 3b Primary Efficacy Endpoint (Estimand 2)

This endpoint is the incidence rate of virologically confirmed COVID-19. The main analysis on this endpoint will be carried out in the Phase 3b mITT and the sensitivity analysis will be performed in the Phase 3b PP analysis set. Incidence rate in each arm will be displayed together with 95% CI.

The statistical hypothesis for this analysis is described in [Section 8.4.2](#).

Definition and handling of intercurrent events is described in [Section 8.3.1](#).

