- l Review of AEs will include surveillance for solicited (only after Day 92 vaccination and only for Phase 2 and 3a) and unsolicited AEs, SAEs, MAAEs, and AEs leading to discontinuation/withdrawal; Solicited AE data will be gathered by Diary for Day 1 through Day 7 for all participants after each of the initial vaccination series only; Unsolicited AE data will be gathered by interview at clinic visits and telephone contacts through Screening and 28 days after each vaccination. SAEs, MAAEs, and AEs leading to discontinuation/withdrawal will be collected at all timepoints after signing of the informed consent.
- m Only participants in Phase 2 and 3a complete a diary after vaccination on Day 92; no diary is completed after vaccination on Day 120. Participants in Phase 1 and 3b do not complete a diary after vaccination on either Day 92 or Day 120.
- n For participants in Phase 1 and Phase 3b, the visit window at Day 92 is +30 days. For participants in Phase 2 and Phase 3a, the visit window at Day 92 is +14 days.

- o Participants ineligible for additional doses (Section 5.1.5) do not have a clinic visit at Day 120 and will not have weekly telephone visits on Day 99 to Day 113 and Days 127 to Day 176 but will have monthly telephone visits instead on Days 120, 150, and 180.

DAY 92 TO END OF STUDY VISIT FOR PHASE 3C PARTICIPANTS

Visit Name	Weekly Study Call	Follow-up Visit	Weekly Study Call	Monthly Study Call	Final Visit	Unscheduled Visit ^b	ET Visit
Visit Type ^a	TC	Clinic	TC	TC	Clinic	Clinic	Clinic
Study Day:	92, 99, 106, 113, 120, 127, 134, 141, 148, 155, 162, 169, 176, 183, 190, 197, 204	211	218, 225, 232, 239, 246, 253, 260	290, 320, 350	394	N/A	N/A
Visit Window (days):	± 2	+30	± 2	± 2	+14	N/A	N/A
Physical examination ^c		X			X	X	X
Vital signs and body temperature ^d		X			X	X	X
Pulse oximetry						X	
Blood sampling ^e		X			X		X
Nasal swab sample for RT-PCR SARS-CoV-2 ^f						X	
Review of Medical History		X			X	X	X
Review for COVID-19 symptoms and risks ^g	X	X	X	X	X	X	X
Adverse events ^h	X	X	X	X	X	X	X
Concomitant medication/vaccines collection	X	X	X	X	X	X	X

Abbreviations: AE=adverse event; COVID-19=coronavirus disease 2019; ET=early termination; MAAE=medically attended adverse event; N/A=not applicable; RT-PCR=reverse transcription polymerase chain reaction; SAE=serious adverse event; SARS-CoV-2=severe acute respiratory syndrome coronavirus 2; TC=telephone call

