Exploratory 4b	COVID-19 with onset at any time after the first dose of study vaccine administration and up to Day 92	ITT + no prior infection (3b & Pooled)	[Last date at risk – Date received 1st dose]+1	No
Exploratory 5a	Severe COVID-19 with onset between Day 36 and Day 92 by specific variant	miITT (3b & Pooled)	[Last date at risk – Date received 1st dose]+1	No
Exploratory 5b	Severe COVID-19 with onset at any time after the first dose of study vaccine administration and up to Day 92	ITT + no prior infection (3b & Pooled)	[Last date at risk – Date received 1st dose]+1	No

\*COVID-19 events will be confirmed, protocol-defined cases. \*\* Where the last date at risk will be defined as COVID-19-event date or censor date, whichever comes first.

(a) Unless specified otherwise, reference to the protocol endpoints is a reference to the Phase 3b endpoints.

Confirmed, protocol-defined COVID-19 cases will be determined by case report form (CRF) data, as confirmed by the blinded Independent Adjudication Committee and adjudicated for severity, with the date of case onset as date of symptom onset and date of positive COVID test date, whichever occurs first. Both protocol-defined and (protocol-defined) severe cases flagged in the CRF will be included in the primary endpoint.

For participants with no covid-event during the time interval the censor date for the last date at risk is whichever of the following comes first:

- Date of completion of Day 92 visit;
- Date of death unrelated to COVID-19;
- Date of receipt of Switchover or receipt of non-study COVID-19 vaccine
- Lost to Follow-up (last known alive date or date of Day 1+91 days, which is earlier).

Section 9.2.2 presents the endpoints and analyses in terms of estimands for primary, secondary and exploratory efficacy analyses.

As a sensitivity analysis of the primary endpoint (Phase 3b only), severe cases and deaths due to COVID-19 will be repeated using all COVID-19 cases from CRF, including those cases that are not confirmed by the blinded Independent Adjudication Committee and with severe or death severity as reported in the CRF.

Day 36 is defined as second dose+7 days (29+7=36 days), and Day 92 is defined as second dose+63 days (29+63=92 days). Another sensitivity analysis of the primary endpoint (Phase 3b only) will be performed using Day 92 visit instead of second dose+63 days.

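### In the main efficacy analysis, events stop counting at second dose + 63 days but event-free participants are censored at the Day 92 visit, so reported surveillance time can include days when no event can count

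*SAP*

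**What the plan says.** All the SAP rules are in Section 6.4, in the text after Table 6.

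- **Event window.** "Day 36 is defined as second dose+7 days (29+7=36 days") and "Day 92 is defined as second dose+63 days (29+63=92 days"). The SAP then adds: "Another sensitivity analysis of the primary endpoint (Phase 3b only) will be performed using Day 92 visit instead of second dose+63 days". The main analysis therefore runs to second dose + 63, and the visit is an alternative cut-off.
- **Censoring.** For participants without an event, "the censor date for the last date at risk is whichever of the following comes first". The list has four items: "Date of completion of Day 92 visit"; non-COVID death; Switchover or a non-study COVID-19 vaccine; and "Lost to Follow-up (last known alive date or date of Day 1+91 days, which is earlier"). Second dose + 63 days is not among them.
- **Use of the result.** SAP Section 6.4.1 computes time at risk as the last date at risk minus (second dose + 7 days), plus 1. It sums this to person-years by arm, shown beside the number of cases, and adds a Kaplan-Meier plot.
- **Visit timing.** Protocol Appendix 1 (Day 92 to end-of-study schedule) says: "For participants in Phase 1 and Phase 3b, the visit window at Day 92 is +30 days". Protocol Section 4.5.3.2 instead places the first Switchover dose at least 56 days (+30 days) after the second dose.

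**The concern.** Cases and person-time should cover the same window. Here the case count closes at second dose + 63, while the clock for an event-free attender runs to the visit. Switchover sets no earlier limit, because that dose is given at the Day 92 visit. The Day 1 + 91 cap applies only to loss to follow-up.

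Three displayed items are exposed:

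- the person-years in the primary efficacy table;
- any rate a reader obtains by dividing cases by those person-years;
- the tail of the Kaplan-Meier curve, which can continue flat past day 57 only because later onsets are not counted.

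A participant whose onset falls after second dose + 63 but before a late visit has no event in the window, and so would also accrue at-risk time after becoming ill.

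**Working it through.** **1. The plan's own figures.** 29 + 7 = 36 and 29 + 63 = 92, as the SAP states. Counting both end days, the window is 63 − 7 + 1 = 57 days. The 372 events for about 90% power also reproduce: Schoenfeld's formula with HR 0.5 against a null of 0.7, one-sided 0.025 and 1:1 allocation gives 372 events (power 0.9006). That figure depends on events, not person-time, so this point does not touch it.

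**2. How late the visit can be.** Let d be the visit date minus (second dose + 63).

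- Appendix 1, with the second dose on Day 29: Day 92 + 30 = Day 122 = second dose + 93, so d is at most 93 − 63 = 30.
- Section 4.5.3.2: 56 to 86 days after the second dose, so d runs from 56 − 63 = −7 to 86 − 63 = 23.

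The two protocol statements give different latest dates and must be reconciled. I take no view on which is intended.

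**3. Person-time per event-free attender.** Days counted = 57 + d; ratio = (57 + d)/57; shortfall in cases per person-year = 1 − 57/(57 + d).

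| d (days) | Days counted | Ratio | Shortfall |
|---|---|---|---|
| 0 | 57 | 1.00 | 0% |
| 7 | 64 | 1.12 | 10.9% |
| 15 | 72 | 1.26 | 20.8% |
| 23 (limit, Section 4.5.3.2) | 80 | 1.40 | 28.75% |
| 30 (limit, Appendix 1) | 87 | 1.53 | 34.5% |

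The shortfall column applies to a whole arm only if every visit has that d. It is then a close approximation, because event-free participants are nearly the whole denominator (372/16,000 = 2.3% with events at the planned numbers). Visits with d below 0 cause no inflation.

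**4. Effect on the primary test.** Every countable event occurs at or before day 57 of time at risk. Follow-up beyond the last possible event time enters no risk set, so the Cox partial likelihood and the log-rank statistic are the same under either rule. The proportion with cases uses no person-time.

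**5. Simulation check.** Assumptions: 16,000 participants, hazards set for about 372 events at HR 0.5, d uniform on 0 to 30 days. One run gave 243 placebo and 117 ARCT-154 cases.

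| | Censored at visit | Capped at second dose + 63 |
|---|---|---|
| Placebo person-years | 1,548.5 | 1,230.4 |
| Placebo cases per 1,000 person-years | 156.9 | 197.5 |
| ARCT-154 cases per 1,000 person-years | 75.0 | 94.4 |
| Cox HR (95% CI) | 0.4777 (0.3832 to 0.5956) | 0.4777 (0.3832 to 0.5956) |
| VE from rate ratio | 52.2% | 52.2% |

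Placebo person-time is inflated by 1,548.5/1,230.4 − 1 = 26%. With d uniform on −7 to 23, a separate run gave 1,396.9 against 1,210.1 placebo person-years (+15%), again with identical HR and CI under both rules.

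**The case against.** **The list may be loosely worded.** SAP Section 5.2 lets Section 6.4 override the visit meaning of Day 92, and Section 6.4 then defines Day 92 as second dose + 63. The authors may have meant the same date in the censoring list. This does not hold on the text: the item names completion of the visit, and the same section treats the visit and second dose + 63 as different cut-offs. A programmer following the list would censor at the visit.

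**No planned incidence estimate is wrong.** This stands. Protocol Section 8.7.3.4 says "Incidence rate in each arm will be displayed together with 95% CI", and a reader might infer that a promised person-time rate will be misreported. The documents do not support that. Protocol Table 18 describes the efficacy display as a proportion, and Section 8.7.3.2 pairs the term incidence rate with Clopper-Pearson intervals. SAP Section 6.4.1 shows a proportion with a Clopper-Pearson interval and plans no cases-per-person-year estimate. What is exposed is the surveillance-time figure and whatever readers compute from it.

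**A coherent version is already planned.** Partly right. The sensitivity analysis moves the event cut-off to the visit, which matches the censoring rule for the Phase 3b primary endpoint. The main analysis stays mismatched.

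**Day 1 + 91 is not itself an error.** This also stands for the ITT endpoints. ITT includes anyone given one dose, and a participant with no second dose has no second dose + 63. For them Day 1 + 91 (1 + 91 = 92) is the workable anchor.

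**Conclusion.** Wrong as written, for the reported surveillance time only. As the text stands, an event-free participant can contribute up to 87 days (Appendix 1 window) or 80 days (Section 4.5.3.2) against a 57-day event window. The average excess cannot be stated, because visit dates are not in the documents. If every visit were 5, 10 or 15 days late (an assumption), person-time would be inflated by 5/57 = 9%, 10/57 = 18% or 15/57 = 26%.

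Two stronger inferences are not supported:

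- **That vaccine efficacy is biased.** The primary HR, CI, VE, log-rank test and the rule that the lower limit must exceed 30% are untouched. With blinded visits, both arms should be inflated about equally.
- **That person-time is inflated by 53%.** That is one participant's maximum under one of two conflicting visit rules, and the other rule allows visits before second dose + 63.

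The exact invariance is shown for the primary endpoint, whose clock starts at second dose + 7. I do not extend it to endpoints timed from the first dose, where the cut-off varies with the second-dose date.

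**What to change.** In SAP Section 6.4:

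- Add second dose + 63 days to the whichever-comes-first list for the main analysis of all endpoints ending at Day 92, for participants who received a second dose.
- For participants with only one dose in the ITT endpoints, state Day 1 + 91 days as the cap.
- Use the Day 92 visit date as the cut-off only in the existing sensitivity analysis.

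Separately, the two protocol statements on Day 92 timing should be reconciled.

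The cost is a short edit to the SAP's censoring list and one derivation, with no new data. Because the change cannot alter the primary test, it can be made late without raising doubt about the efficacy conclusion.

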	antinucleocapsid antibody or neutralizing antibody (as assessed by sVNT for Phase 1/2/3a and MNT for Phase 3c) indicating exposure to SARS-CoV-2 prior to vaccination or SARS-CoV-2 infection prior to 7 days (inclusive) after the second study vaccination dose (Day 35).	other COVID-19 positive test or seropositivity for anti-nucleocapsid antibody indicating exposure to SARS-CoV-2 prior to vaccination or SARS-CoV-2 infection prior to 7 days (inclusive) after the second study vaccination dose (Day 35).  Note: This also impacts mITT and IAS analysis sets definitions where IcEv3 is considered.	assessment of early infection
Section 8.3.1 Table 15 (estimand 1 – Rationale for Strategies)	IcEv4 and IcEv5 could also be potentially confounding but it is more difficult to determine the precise timing of these events, so a principal stratum strategy is used to exclude these participants from immunogenicity analyses.	IcEv4 and IcEv3 could also be potentially confounding but it is more difficult to determine the precise timing of these events, so a principal stratum strategy is used to exclude these participants from immunogenicity analyses.	Correction
Section 8.3.1 Table 17 (estimand 3 – unsolicited Aes - Intercurrent Event (IcEv) Strategy)	Intercurrent Event (IcEv) Strategy:  IcEv2 (Non-study vaccine): treatment policy strategy  IcEv5 (Confounding On-study Medications): composite strategy	IcEv2 (Non-study vaccine): while on treatment strategy  IcEv5 (Confounding On-study Medications): treatment policy strategy	IcEv2: Correction of the name of the strategy to reflect the fact that events occurring after IcEv2 will not be included in the analysis as specified in protocol  IcEv5: Correction of the name of the strategy to reflect the fact that events occurring after IcEv5 are included in the analysis as specified in the protocol
Section 8.3.1 Table 17 (estimand 4 – Reactogenicity - Rationale for Strategies)	Events occurring after IcEv2, IcEv3 and IcEv5 could contribute spurious reactogenicity data so a treatment policy is used for these events and events occurring after	All solicited events will be analyzed regardless of occurrence of intercurrent events.	Reactogenicity is participant reported outcome, which will be analyzed as it is without modification.

	these IcEv's will be summarized separately		

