Section 8.7.2 Table 18 estimand 2 (efficacy)	Imputation/Data/Censoring Rules: For deaths unrelated to COVID-19, censor at date of death. For participants who undergo Switchover/Further Study Vaccine or receive a non-study COVID-19 vaccine, censor at date of Switchover or non-study vaccination.	Participants last date at risk date will also be censored for Lost to Follow-up	Add rule of handing censoring condition for lost to follow-up scenario.
Section 8.7.2 Table 18 estimand 2 (efficacy)	Sensitivity: the same analysis will be performed in the Pooled mITT and Phase 3b PP analysis sets.	
2 additional sensitivity analyses to be performed.
 
 
• A sensitivity analysis of all Covid cases reported in CRF and not confirmed by the blinded Independent Adjudication Committee or with severity as reported in the CRF has been added for the primary endpoint, severe cases and deaths due to COVID-19.
 
• Day 36 is defined as second dose+7 days (29+7=36 days), and Day 92 is defined as second dose+63 days (29+63=92 days). Another sensitivity analysis of the primary endpoint (Phase 3b only) will be performed using Day 92 visit instead of second dose+63 days.
 
	Add additional sensitivity analyses to assess the robustness of the primary analysis results.
Section 8.7.2 Table 18 estimand 3 (safety)	Supportive: Analysis will be performed for different time intervals, specifically:	As per section 6.6.1.3 of this SAP, only the following intervals will be done:	To summarize study periods that are not overlapping

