Section 8.3.1 Table 16 Estimands for Primary, Secondary and Exploratory Efficacy Analyses	
IcEv1 (Death not due to COVID-19): Hypothetical strategy
 
IcEv2 (Non-study COVID-19 vaccine):
 
IcEv3 (Early infection): Principal stratum strategy
 
IcEv4 (Study infection): Composite strategy
 
IcEv5 (Confounding On-study Medications): Hypothetical strategy
	
IcEv1 (Death not due to COVID-19): Treatment policy strategy
 
IcEv2 (Non-study COVID-19 vaccine): Treatment policy strategy
 
IcEv3 (Early infection): Principal stratum strategy for analyses where events only counted from 7 days after second vaccination
 
Composite strategy where events counted at any time after first vaccination
 
IcEv4 (Study infection): Composite strategy
 
IcEv5 (Confounding On-study Medications): Treatment policy strategy
	Correction of errors
Section Section 8.3.1 Table 16 (estimand 2 – Estimand Description)	
The proportion of participants (and 95% confidence interval) with virologically confirmed COVID-19 (Appendix 2) detected after 7 days post the second study vaccine dose.
 
Proportion of participants (and 95% confidence interval) with virologically confirmed COVID-19 (Appendix 2) detected at any time after first vaccine dose
	
VE estimated as 1-HR, where HR is the hazard ratio from the adjusted Cox Proportional Hazard model for virologically confirmed COVID-19 detected after 7 days post the second study vaccine dose.
 
VE estimated as 1-HR, where HR is the hazard ratio from the adjusted Cox Proportional Hazard model for virologically confirmed COVID-19 detected at any time after first vaccine dose
	Correction made in the SAP to align with planned analysis method

Protocol Section	Analysis method described originally in the protocol	Planned Analysis	Reasons of changes
Section 8.3.1 - Table 17 (estimand 3 - rationale for strategies)	Events occurring after IcEv2 could contribute spurious safety data so a treatment policy is used for these events and events occurring after this IcEv's will be summarized separately. Sensitivity analyses will be conducted in the ITT population where these events will be included (composite strategy).	No Sensitivity analysis of unsolicited AEs for ITT analysis set will be produced	Statistical analysis of safety data will be based on the Phase 1/2/3a SAS and Phase 2/3a SAS and reactogenicity analysis set (RAS).

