8.3.1 Table 17 Estimands for Primary Safety Analyses	Estimand 4, IcEv1 (Death): Composite strategy	Amended to Treatment policy strategy	Correction of error
Section 8.3.1 Table 17 (estimand 4 - Reactogenicity)	Events occurring after non-study vaccine administration or early COVID-19 infection could contribute spurious reactogenicity data, so only the events occurring prior the non-study vaccine administration or early COVID-19 infection will be included in the analysis. Events occurring after these will be summarized separately.	In SAP part 2, it was specified that no censoring of events after receipt of non-study COVID-19 vaccine would be performed. All events were to be presented, irrespective of whether non-study vaccine was received. This rule will be applied in this final SAP i.e. a Treatment policy strategy will be applied for IcEv2.	Randomization should ensure no imbalance in the number of participants receiving non-study COVID-19 vaccine.
Section 8.4.2 Phase 3b Primary hypothesis	VE is estimated as 1-HR, where HR is the hazard ratio from the adjusted Cox Proportional Hazard model, and will be presented together with 95% CIs. The primary efficacy objective will be met if the lower limit of the 95% CI for VE exceeds 30%.	VE is estimated as 1-HR, where HR is the hazard ratio from the adjusted Cox Proportional Hazard model, and will be presented together with 95% CIs. The primary efficacy objective will be met if the lower limit of the 95% CI for VE exceeds 30%. The secondary efficacy objectives will be met if the lower limit of the 95% CI for VE exceeds 0%.	Add the hypothesis testing for the secondary efficacy objectives.
Section 8.6 Subgroups	Subgroups for which immunogenicity, safety and efficacy may be evaluated: -Sex -Age group -Risk group	Subgroups for which immunogenicity, safety and efficacy may be evaluated: -Sex -Age group -Risk group	Exclude "Race/ethnicity" from the subgroup analysis, as the majority of participants (>90%) belong to one ethnicity (Kihm).

Protocol Section	Analysis method described originally in the protocol	Planned Analysis	Reasons of changes
	-Race/ethnicity	-Region of study sites	Add “Region of study sites” in the subgroup analysis due to the heterogeneity of background risk among different sites.

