### 9.2.2 Estimands for Phase 1/2/3a, Phase 3b, and Pooled Primary, Secondary and Exploratory Efficacy Analyses

Estimand Label	Protocol Estimand 2 (Vaccine Efficacy)
Estimand Description	
 
VE estimated as 1-HR, where HR is the hazard ratio from the adjusted Cox Proportional Hazard model for virologically confirmed COVID-19 detected after 7 days post the second study vaccine dose.
 
VE estimated as 1-HR, where HR is the hazard ratio from the adjusted Cox Proportional Hazard model for virologically confirmed COVID-19 detected at any time after first vaccine dose
 

Target Population	Eligible participants who have received both doses of study vaccine in the initial series. The population includes participants without evidence of COVID-19, SARS-CoV-2 infection, or nucleocapsid antibody positivity on or prior to Day 35.
Endpoint	
VE for COVID-19/severe COVID 19/death due to COVID-19 (dependent on the endpoint concerned) detected after 7 days post the second study vaccine dose and based upon virologically confirmed COVID-19, estimated as 1-HR, where HR is the hazard ratio from the adjusted Cox Proportional Hazard model
 
Additional endpoints will include VE for virologically confirmed COVID-19 detected at any time after first vaccine dose estimated as 1-HR, where HR is the hazard ratio from the adjusted Cox Proportional Hazard model.

Treatment Conditions	ARCT-154 dose 5 µg or placebo administered on Day 1 and Day 29.
Population-Level Summary	See 'Endpoint' above
Intercurrent Event (IcEv) Strategy	

 
• IcEv1 (Death not due to COVID-19)
 
	Treatment policy strategy

 
• IcEv2 (Non-study COVID-19 vaccine)
 
	Treatment policy strategy

 
• IcEv3 (Early infection)
 
	
Principal stratum strategy for analyses where events only counted from 7 days after second vaccination
 
Composite strategy where events counted at any time after first vaccination

 
• IcEv4 (Study infection)
 
	Composite strategy

 
• IcEv5 (Confounding On-study Medications)
 
	Treatment policy strategy

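### The primary vaccine efficacy estimand is labelled treatment policy for outside vaccination and unrelated death, but the Cox analysis censors at both, and SAP 6.4 does not say clearly whether cases are censored too

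*SAP*

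**What the plan says.** Protocol Table 16 (Section 8.3.1) assigns the hypothetical strategy to death not due to COVID-19 (IcEv1) and to non-study COVID-19 vaccine (IcEv2) in the VE estimand. Protocol Table 18 (Section 8.7.2) censors at both.

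SAP 7.2 changes both labels to treatment policy, giving the reason "Correction of errors". SAP 9.2.2 carries the new label, "Treatment policy strategy", for IcEv1 and IcEv2 and also for IcEv5 (confounding medication).

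The censoring did not follow the label. SAP 7.1 restates the Table 18 rule and only adds to it: "Participants last date at risk date will also be censored for Lost to Follow-up". Under Table 6, SAP 6.4 lists unrelated death and "Date of receipt of Switchover or receipt of non-study COVID-19 vaccine" among the censor dates. That list is introduced with "For participants with no covid-event during the time interval the censor date for the last date at risk". The Table 6 footnote and SAP 6.4.1 then define the last date at risk as the earlier of the event date and the censor date.

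**The concern.** A treatment policy estimand for outside vaccination means that follow-up and cases after it are used. A Cox model that censors there estimates the effect in the absence of outside vaccination, provided the censoring is non-informative. A reader of SAP 9.2.2 would take the primary VE as the first quantity when the analysis delivers the second, and the SAP does not state the assumption the second one needs.

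The lead-in to the censor list raises a further question. If only non-cases receive a censor date, someone who is vaccinated outside and then becomes a case before Day 92 still counts, while a comparable participant who stays well leaves the risk set at vaccination. The mITT definition in SAP 4.1 does not remove outside vaccinees, so the primary analysis is exposed to both problems.

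**Working it through.** **1. Labels against handling**

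| Estimand (SAP) | Handling after IcEv2 | Label |
|---|---|---|
| 1, immunogenicity (9.2.1) | later data censored | while on treatment |
| 3, unsolicited events (7.1, 9.2.3) | later events left out | while on treatment |
| 4, solicited events (7.2, 9.2.3) | later events kept | treatment policy |
| 2, VE (6.4, 9.2.2) | censored | treatment policy |

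For Estimand 3 the SAP explains its relabelling: "Correction of the name of the strategy to reflect the fact that events occurring after IcEv2 will not be included in the analysis". For Estimand 4, where nothing is censored, it says: "This rule will be applied in this final SAP i.e. a Treatment policy strategy will be applied for IcEv2". By the SAP's own usage, Estimand 2 is the odd one out. IcEv5 in Estimand 2 is consistent: it is labelled treatment policy and is not on the censor list.

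**2. Does any planned VE analysis follow people past outside vaccination?** None is stated.
- The sensitivity runs in SAP 6.4 and 6.4.1.1 change the case source, the Day 92 definition or the analysis set, and give no other censoring rule.
- Secondary and exploratory endpoints use the primary method (6.4.2, 6.4.3).
- The per-protocol efficacy set excludes anyone vaccinated outside up to Day 92 (4.1).
- The case frequency tables (6.4) and the comparison of proportions (6.4.1) state no such censoring, but they are not the VE estimate.

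**3. Who has a censor date?** The lead-in in SAP 6.4 names only non-cases. Taking the earlier of two dates makes sense only if a case can also have a censor date, and Protocol Table 18 is not limited to non-cases. The weight of the text favours censoring everyone, but the lead-in says otherwise.

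**4. Size**

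The plan's own figure (SAP 6.1, 6.2.3): 4 × (1.960 + 1.282)² / [ln(0.5/0.7)]² = 4 × 10.507 / 0.11321 = 371.2, rounded up to 372 events for about 90% power. This is reproduced and not disputed.

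Inputs from the plan: VE 50%, 8,000 per arm, 372 events, and a window W = 92 − 36 + 1 = 57 days. Uptake is assumed. The upper values borrow the 20–25% Phase 3c dropout allowance in Protocol 8.5.3. Exclusion 10 in Protocol 5.1.2 bars people planning outside vaccination, so true Phase 3b uptake may be lower.

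Let u be the uptake, spread evenly over W, e the outside vaccine's protection and L the lag to protection. The protected share of person-time is p = u(W − L)²/(2W²). Subscript P is placebo and A is ARCT-154. For rare events:
- censoring everyone: VE = 50%
- no censoring at outside vaccination: VE = 1 − 0.5 × (1 − p_A e_A)/(1 − p_P e_P)
- literal rule: the same hazard ratio multiplied by (1 − u_P/2)/(1 − u_A/2)

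With uptake 25% on placebo, 15% on ARCT-154 and e = 0, the literal rule gives 1 − 0.5 × 0.875/0.925 = 52.7%. Reversed, it gives 1 − 0.5 × 0.925/0.875 = 47.1%. With 25% in both arms, L = 14 and e = 0.8 on placebo only, p = 0.25 × 43²/(2 × 57²) = 0.0711. Both the literal rule and no censoring then give 1 − 0.5/(1 − 0.0711 × 0.8) = 47.0%.

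A Cox simulation (8,000 per arm, about 372 events, 1,500 runs, Monte Carlo SE about 0.15 points) agrees:

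| Uptake placebo / ARCT-154 | Outside vaccine | Censor all | Literal | No censoring |
|---|---|---|---|---|
| 25% / 25% | 80% in both arms, 14-day lag | 50.2 | 50.2 | 50.2 |
| 25% / 15% | no effect | 50.0 | 52.8 | 50.0 |
| 15% / 25% | no effect | 50.0 | 47.1 | 50.0 |
| 25% / 25% | 80% on placebo only, 14-day lag | 50.1 | 47.1 | 47.1 |

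The readings part from full censoring when uptake differs by arm or when the outside vaccine's relative benefit does. The lowest no-censoring value tried (25% uptake, 80% protection on placebo only, no lag) is 1 − 0.5/(1 − 0.125 × 0.8) = 44.4%. With 372 events the success rule needs an observed VE of about 43.3%: HR 0.567 splits the events about 135 to 237, SE = √(1/135 + 1/237) = 0.108, and ln 0.7 − 1.96 × 0.108 = −0.568, so HR = 0.567.

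For IcEv1 there is nothing to compute, because no case can follow death.

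**The case against.** The strongest reply is that this is wording. The censoring rule is the same in Protocol Table 18, SAP 7.1 and SAP 6.4, so programmers would probably censor everyone, and the VE would then be unaffected. Observer-blinding (SAP 2.4), with no unblinding of those who leave for another vaccine except for certain serious events (Protocol 6.6.1), makes unequal uptake less likely. Much of this stands. It limits the likely size, but it does not make the label right or remove the ambiguity.

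It can also be said that *while on treatment*, the SAP's name for this handling elsewhere, would serve as well as *hypothetical*. The essential point is that *treatment policy* must go. Restoring the protocol's term is the smaller change.

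Three stronger readings might be inferred, and the documents do not support them:
- **That outside vaccination by arm will go unreported.** SAP 4.1 makes it a major deviation for the per-protocol efficacy set, and SAP 4.2 and 6.3.1 summarise exclusion reasons by group.
- **That the SAP defends the VE analysis by appeal to randomization.** The sentence "Randomization should ensure no imbalance in the number of participants receiving non-study COVID-19 vaccine" is the reason given for solicited adverse events, not for VE.
- **That the literal rule can never match a recognised estimand.** With equal uptake it gave the same VE as no censoring in both scenarios run (50.2% and 47.1%).

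**Conclusion.** The label is wrong as written. SAP 7.2 and 9.2.2 contradict SAP 6.4, SAP 7.1 and Protocol Table 18, and the SAP's own use of the terms confirms it. This needs no assumption. For IcEv1 it is a matter of naming only. For IcEv2 it changes what the headline VE may be said to estimate.

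The counting rule is an ambiguity. It would be too strong to say that the SAP plans to count cases after outside vaccination, because the earlier-date rule and Table 18 point the other way.

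The effect on VE cannot be determined, since the documents give no Phase 3b uptake. The shifts shown rest on assumed uptake and protection, a true VE of 50% and vaccination spread evenly over the window. Under those assumptions none takes VE below about 43.3%, so none would by itself reverse the primary decision. The 372 events and 90% power are unaffected. This should be fixed, but it is not a threat to the trial's conclusion on the evidence available.

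**What to change.** 1. **SAP 9.2.2 and 7.2.** Restore *hypothetical* for IcEv1 and IcEv2 in Estimand 2, leave IcEv5 as it is, and state that the estimate assumes non-informative censoring.
2. **SAP 6.4.** State that the censor date applies to all participants, cases included, as in Protocol Table 18. State which rule the already unblinded Phase 3b analysis (SAP 2.5) used, and report any difference in cases and VE.
3. **Reporting.** Show the by-arm count of non-study vaccination before Day 92, already planned in another form, beside the primary VE in the mITT set. Add one supplementary Cox run in the full mITT set, labelled post hoc, that does not censor at non-study vaccination but still censors at unrelated death, switchover, loss to follow-up or Day 92.

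The cost is a few lines of SAP text, one displayed count and one model run. No new data are needed: Protocol 5.2.3 asks outside vaccinees to continue study procedures, and Phase 3b swabs stop only after Day 92 (Protocol 4.5.3.7). Participants who left the study to be vaccinated elsewhere remain censored, so the extra run is only partly a treatment policy analysis and should say so. The primary VE changes only if the unblinded analysis counted cases after outside vaccination.
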